Disease response is evaluated according to the clinico-haematological ELN criteria [1] after 3 and 6 cycles (i.e. at weeks 12 and 24, respectively) of treatment with Givinostat for both parts of the Study. All phlebotomies performed in the first 3 weeks of treatment are not been counted to assess the clinico-haematological response.

The Study will last up to a maximum of 24 weeks of treatment. However, after completion of the trial, all patients achieving clinical benefit are allowed to continue treatment with Givinostat (at the same dose and schedule) in a long-term study (Study N.: DSC/11/2357/44), providing that the long-term study has already received all necessary approvals in that specific country and site, and the study has already been initiated in that particular site.

Safety is monitored at each visit throughout the entire duration of the Study. Treatment is administered on an outpatient basis and patients are followed regularly with physical and laboratory tests, as specified in the protocol (see [Appendix A](#) and [paragraph 4.5.4](#) of the Study protocol version 3.0); in case of hospitalization, the treatment is continued or interrupted according to the Investigators’ decision.

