5.2. INTENT-TO-TREAT ANALYSIS SET (ITT)

The Intent-to-treat analysis set will include all recruited patients who receive at least one dose of study medication and from whom at least one post-baseline efficacy measurement is obtained.

Of note, patients who dropped the study due to drug-related TEAE(s) before that the post-baseline efficacy measurement is obtained (i.e. at C3D28 and/or at C6D28), will be considered in the ITT analysis set; in these cases, the post-baseline efficacy measurements (i.e. at C3D28 and/or at C6D28) will be considered as “No Response”, even if these assessments were not performed.

In addition, patients who have performed the visit when the post-baseline efficacy measurements (i.e. at C3D28 and/or at C6D28) had to be performed, but for which the following conditions will happen, will be excluded from the ITT analysis set:

- HCT > 45% or HCT ≤ 45% with phlebotomy(ies), AND
- at least 2 out of 4 assessments of the following will be not performed:
 - a) WBC count;

Document: PPD

Author: PPD

Version Number:

V2.2

Version Date:

21 March 2018

Template No: CS_TP_BS016 – Revision 3

Reference: CS_WI_BS005

Effective Date: 01May2012

Copyright © 2012 Quintiles Transnational Corp. All rights reserved.

The contents of this document are confidential and proprietary to Quintiles Transnational Corp. Unauthorized use, disclosure or reproduction is strictly prohibited.

- b) PLT count;
- c) Spleen evaluation by CT scan or MRI;
- d) Disease-related assessment by MPN-SAF.

This is due to the fact that is not possible to define a clinico-haematological response as per ELN response criteria in these cases.

All efficacy analyses will be conducted on this population and will be based on the *effective/actual* DL/daily doses of Givinostat at which each patient has been treated.

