13.1. NON-DRUGS THERAPIES

Prior and significant non-drug therapies (e.g. phlebotomies, transfusions) to treat PV will include regimens discontinued up to 24 weeks prior to enrolment. Non-drug-therapies will be summarised by type of procedure (i.e. transfusion, phlebotomy, other), date of procedure, reason for procedure. Non-drug therapies (e.g. transfusion, phlebotomy) will be presented for the SAF analysis set.

See [Appendix 2](#) for handling of partial dates for non-drugs therapies, in the case where it is not possible to define a non-drug therapy as prior, concomitant, or post treatment, the non-drug therapy will be classified by the worst case (i.e. concomitant non-drug therapy):

- 'Prior' non-drug therapies are defined as those starting and ending prior to the first administration of investigational Study drug (i.e. C1D1).
- 'Concomitant' non-drug therapies are defined as those started at or after first administration of Study drug (i.e. C1D1) and include those started prior to the first administration of investigational Study drug (i.e. C1D1) but continued during the Study.
- 'Post' non-drug therapies are non-drug therapies which started after the last Study drug intake.

Frequency tabulations will be also presented for significant non-drug therapies.

Notably, all phlebotomies performed in the first 3 weeks of treatment will be not counted to assess the clinico-haematological response according to the clinico-haematological ELN response criteria [\[1\]](#) at C3D28 and at C3D28 in **Parts A** and **B**.

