16.3. CRITERIA FOR ASSESSING CLINICO-HAEMATOLOGICAL IMPROVEMENT

Disease response will be evaluated according to the following clinico-haematological ELN criteria [1] after 3 and 6 cycles (i.e. at weeks 12 and 24, respectively) of treatment with Givinostat both in **Part A** (exploratory endpoints) and in **Part B** (primary and secondary endpoints, respectively).

- **Complete response:**
 1. HCT < 45% without phlebotomy, and
 2. Platelets $\leq 400 \times 10^9/L$, and
 3. WBC $\leq 10 \times 10^9/L$, and
 4. Normal spleen size, and
 5. No disease-related systemic symptoms (i.e. pruritus, headache, microvascular disturbances).

- **Partial response:**

Patients who do not fulfil the criteria for complete response and

 1. HCT < 45% without phlebotomy, or
 2. Response in 3 or more of the other criteria.

- **No response:** any response that does not satisfy partial response.

Only in case the enrolment in **Part A** is slow (i.e. < **5 patients enrolled in 3 months**) and the eligibility for this part of the study may be expanded to all patients with cMPN, disease response for this part of the study can be evaluated according to the clinico-haematological ELN and EUMNET criteria [7] after 3 and 6 cycles of treatment with Givinostat, in ET and MF patients, respectively.

For ET (from the clinico-haematological ELN response criteria):

Document: PPD

Author: PPD

Version Number:

V2.2

Version Date:

21 March 2018

Template No: CS_TP_BS016 – Revision 3

Reference: CS_WI_BS005

Effective Date: 01May2012

Copyright © 2012 Quintiles Transnational Corp. All rights reserved.

The contents of this document are confidential and proprietary to Quintiles Transnational Corp. Unauthorized use, disclosure or reproduction is strictly prohibited.

- **Complete response:**
 1. Platelets $\leq 400 \times 10^9/L$, **and**
 2. No disease related systemic symptoms (i.e. pruritus, headache, microvascular disturbances), **and**
 3. Normal spleen size, **and**
 4. WBC $\leq 10 \times 10^9/L$.

- **Partial response:**

Patients who do not fulfil the criteria for complete response and

 1. Platelet count $< 600 \times 10^9/L$, **or**
 2. Platelet count decrease $> 50\%$ from baseline.

- **No response:** any response that does not satisfy partial response.

Both for PV and ET patients, all phlebotomies performed in the first 3 weeks of treatment are **not** counted to assess the clinico-haematological response.

For MF (from EUMNET response criteria)

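### The ITT exclusion in SAP 5.2 omits the 3-week phlebotomy exemption, so read literally it can remove a patient who is a certain responder under 16.3

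*SAP*

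**What the plan says.** **The exclusion (SAP 5.2).** A patient who attended the visit at which response was due (C3D28 and/or C6D28) leaves the ITT set if two conditions hold together:

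- on haematocrit, "HCT > 45% or HCT ≤ 45% with phlebotomy(ies), AND"
- on the rest, "at least 2 out of 4 assessments of the following will be not performed", the four being WBC count, platelet count, spleen imaging and MPN-SAF.

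The reason given is: "This is due to the fact that is not possible to define a clinico-haematological response as per ELN response criteria in these cases". This set serves for every efficacy analysis, and the PP set (5.3) is drawn from it.

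**The response rule (SAP 16.3).** A patient who misses complete response is a partial responder by either of two routes. The first is "HCT < 45% without phlebotomy, or"; the second is "Response in 3 or more of the other criteria".

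**The early-phlebotomy exemption.** It appears three times, each time for the assessment of response. Section 3.1: "All phlebotomies performed in the first 3 weeks of treatment are not been counted to assess the clinico-haematological response". Section 13.1: "all phlebotomies performed in the first 3 weeks of treatment will be not counted". Section 16.3 gives the same rule for PV and ET, beginning "all phlebotomies performed in the first 3 weeks of treatment are" and going on to discount them. Section 5.2 neither repeats the exemption nor refers to it.

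**The concern.** The haematocrit condition in 5.2 is meant to pick out patients who cannot qualify through the haematocrit route, so that their response depends on the other four items. That works only if phlebotomy means the same thing in 5.2 as in 16.3. On the literal text it does not. A patient phlebotomised once in week 2, with haematocrit below 45% at C3D28, satisfies the haematocrit route in 16.3, yet also falls under the words of 5.2 if two other items are missing. The reason given for exclusion is then untrue of that patient.

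Part B is decided by counts of responders (SAP 3.5), so membership of the primary set matters patient by patient. Nothing later restores the patient. PP is a subset of ITT, and the investigator override (16.3, 17.2) concerns the response category, not set membership.

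**Working it through.** **1. Is the patient's response really undefined?** Take haematocrit below 45% with phlebotomies only in weeks 1-3, so the haematocrit criterion of 16.3 is met. Each of the other four items is met, not met or missing. The patterns with at least two missing number

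C(4,2)·2² + C(4,3)·2 + 1 = 24 + 8 + 1 = 33.

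Each pattern was classified under 16.3 over every possible value of the missing items:

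| Haematocrit criterion | Certain PR | CR or PR | NR or PR | Certain NR |
|---|---|---|---|---|
| Met (early phlebotomy only) | 22 | 11 | 0 | 0 |
| Not met | 0 | 0 | 27 | 6 |

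In the first row every pattern is a responder for the CR + PR rate. In 11 only the grade is open. The literal 5.2 excludes all 33; with the 3-week exemption it excludes none. In the second row, the 6 certain non-responders have two items missing and both observed items failing.

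**2. Reproducing the design (SAP 3.5).** Inputs: 12 patients in Stage 1, stop at 6 or fewer responders; 28 in total, reject the null at 18 or more. With X ~ Bin(12, p) and Y ~ Bin(16, p):

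- early termination at p = 0.50: P(X ≤ 6) = 0.6128 (SAP 0.613)
- expected size at p = 0.50: 12 + (1 − 0.6128)·16 = 18.2 (SAP 18.2)
- P(X ≥ 7, X + Y ≥ 18) = 0.0815 at p = 0.50 (SAP 0.081) and 0.9017 at p = 0.75 (SAP 0.902).

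**3. Size of one deletion, as a forced worst case.** Assume exactly one responder is removed, the Stage 1 decision is unaffected and the count of 18 still applies. Then 18/28 becomes 17/27, and the final decision changes only if the true total was exactly 18:

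P(X ≥ 7, X + Y = 18) = P(X ≥ 7, X + Y ≥ 18) − P(X ≥ 7, X + Y ≥ 19)

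- p = 0.75: 0.9017 − 0.8429 = 0.0588, about 0.059
- p = 0.50: 0.0815 − 0.0407 = 0.0407 before rounding of the terms, about 0.041.

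Forcing the deletion therefore lowers the rejection probability under both hypotheses: power from 0.902 to 0.843, type I error from 0.081 to 0.041. This error cannot produce a false positive.

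**The case against.** **The exemption may carry over.** The haematocrit line in 16.3 has no time limit of its own either; the exemption comes from a separate general sentence. Section 5.2 is nearly the complement of that line and appeals to the ELN criteria, so a reader could apply the exemption to both, and then no responder is lost. This reading is plausible, and 5.2 does not say that any phlebotomy counts. But the exemption is stated only for assessing response, not for set membership, and a programmer following 5.2 as written would delete the patient. The objection shows that two readings exist. It does not settle which one applies.

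**The Data Review Meeting (SAP 5) would see it.** Exclusions are agreed before lock, and the reasons are tabulated and listed. That makes a silent deletion less likely, but 5.2 is still the criterion the meeting is given.

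**The case is narrow.** This stands. Section 16.8 places haematocrit, WBC and platelets in one haematology examination, so with a haematocrit result in hand the two missing items would normally be spleen imaging and MPN-SAF.

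**Stronger readings a reader might infer.** One is that the study loses power, to 0.843 with one deletion or 0.741 with two. Those figures require a deletion in every trial, and the SAP supports no such rate. Another is that, because response needs haematocrit below 45% while the exclusion starts above 45%, the exclusion should be moved to 45% or above. That would newly exclude unphlebotomised patients at exactly 45%, some of whom are certain non-responders (the 6 patterns above) and belong in the denominator.

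**Conclusion.** The point holds as a gap in the wording of the primary analysis set. Taken literally, 5.2 removes from ITT and PP a patient whom 16.3 makes a certain responder, on a ground that is false for that patient.

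The practical size is probably small. It needs a patient with only week 1-3 phlebotomies, haematocrit below 45% and at least two of four items missing. The SAP gives no figure for how many would qualify, so no expected loss can be calculated. The bias is against the drug. The probabilities of 0.059 and 0.041 are conditional on one deletion being forced with the Stage 1 decision unaffected, and they assume that the count of 18 is kept for 27 patients. They should not be read as a forecast.

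**What to change.** Add one clause to the haematocrit condition in 5.2: phlebotomies performed in the first 3 weeks of treatment are not counted for this condition, as in 16.3. State the consequence as well: a patient with haematocrit below 45% and only such phlebotomies stays in ITT and is scored as at least PR.

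Leave the haematocrit cut-off in the exclusion where it is. With the clause added, a patient at exactly 45% with only early phlebotomies also stays in ITT, as an unphlebotomised patient at 45% already does. Neither meets the haematocrit criterion.

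The cost is one line of SAP text. Dates of procedures are already summarised under 13.1, so no new data are needed, and the change carries over a rule that the SAP already applies to response.

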3.2. PART A

Part A is the dose escalation part of this Study, evaluating the safety, tolerability and MTD of Givinostat in patients with JAK2^{V617F} positive PV.

In this part of the Study the first cycle of treatment is used to assess the safety and tolerability of Givinostat as well as PK/PD.

After the completion of the first cycle, the patients are treated for an additional 5 cycles.

Only PV patients from Part A assigned to the dose selected for Part B (MTD) can be counted towards the efficacy assessment in Part B.

The Dose Levels and the rules of escalation to the next dose are detailed in [Sections 4.1.1.3](#) and [4.1.1.4](#)

Document: PPD

Author: PPD

Version Number:

V2.2

Version Date:

21 March 2018

Template No: CS_TP_BS016 – Revision 3

Reference: CS_WI_BS005

Effective Date: 01May2012

Copyright © 2012 Quintiles Transnational Corp. All rights reserved.

The contents of this document are confidential and proprietary to Quintiles Transnational Corp. Unauthorized use, disclosure or reproduction is strictly prohibited.

of the Study protocol version 3.0 (see pages 46 and 47).

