3.2.2.3. DEFINITION OF MTD

If 2 or more patients per DL experienced a DLT, dose escalation is terminated and the MTD is the next lower DL if no more than one out of 6 patients have a DLT at that level. Once all patients enrolled in **Part A** are treated for at least 1 cycle, the study team determine the MTD to be used in **Part B** based on the safety and tolerability profile of Givinostat observed as well as the PK and PD data, if applicable.

No intra-patient dose escalation is permitted prior to determining the MTD.

At that time, patients on treatment at lower DLs can be allowed to escalate their Givinostat dose up to the MTD for the remainder part of the study (**Part A**) at the discretion of the Investigator and, after the

Document PPD

Author: PPD

Version Number:

V2.2

Version Date:

21 March 2018

Template No: CS_TP_BS016 – Revision 3

Reference: CS_WI_BS005

Effective Date: 01May2012

Copyright © 2012 Quintiles Transnational Corp. All rights reserved.

The contents of this document are confidential and proprietary to Quintiles Transnational Corp. Unauthorized use, disclosure or reproduction is strictly prohibited.

Sponsor's written authorization. Of note, patients initially dosed at lower DLs that are allowed to escalate their Givinostat dose up to the MTD for the remainder part of the study (**Part A**), are to follow the dose modification rules of **Part B** (see [paragraph 4.3.3.2](#) of the Study protocol version 3.0). Total daily dose can never exceed the MTD defined in **Part A** (i.e. 100 mg b.i.d.).

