In **Part B**, the lowest dosage of Givinostat that can be dispensed to the patients is 50 mg b.i.d., while the highest dosage of Givinostat that could be dispensed to the patients is 100 mg b.i.d. In all the possible dosages (i.e. 50 mg b.i.d., 75 mg b.i.d., 100 mg b.i.d.), patients should self-administer daily Givinostat capsules at home at morning and in the evening (i.e. after 12 hours) with fluids and between meals (i.e. to take the study drug at least 2 two hours after the last meal, or no less than 1 hour before the meal).

Dose adjustments are permitted for patients who do not tolerate the Study protocol-specified dosing schedule, in order to allow to these patients to continue the treatment with Givinostat. The guidelines described in the Study protocol (see [paragraph 4.3.3.2.1](#) and [paragraph 4.3.3.2.2](#) of the Study protocol version 3.0) need to be followed. The objective of the Givinostat dose adjustment rules are to optimize the response for each individual patient, avoiding specific drug-related toxicities. Therefore, dose reductions or interruptions are mandated for specific toxicities and dose increases after an initial dose reduction are allowed in the case of inadequate efficacy at the reduced dosage.

Each dose modification is to be recorded on the Case Report Form (CRF).

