5. Addition of the Contract Manufacturing Organization (CMO) as possible delegate for the management of the Study drug (e.g. secondary packaging, distribution to the sites).
6. Clarification of the meaning of “*any other investigational drug or device*” (i.e. exclusion criterion n. 19).
7. Specification of the instructions related to the Study drug administration and dispensing.
8. Clarification of the fact that no spleen evaluation should be performed in splenectomised patients, while the spleen evaluation was requested in all other patients in **Part B**, since the presence of splenomegaly was one of the parameters to evaluate as per primary objectives of **Part B** (i.e. according to the ELN response criteria [\[1\]](#)).
9. Explanation of the fact that, in case the patient completed the Study (i.e. performed all the evaluations requested to be done at Day 28 of Cycle 6), the evaluations performed at Cycle 6 Day 28 visit were also counted for the End of Study visit.
10. Specification of the fact that, in case the patient completed the Study (i.e. performs all the evaluations requested to be done at the Day 28 of Cycle 6) and she/he was eligible to continue the Study drug treatment in the long-term study (i.e. Study DSC/11/2357/44), the evaluation performed at the Day 28 of Cycle 6 visit of this Study could be also counted for the pre-treatment evaluations of the Study DSC/11/2357/44, provided that no difference in the evaluations was present between the two studies (e.g. haematological and biochemical evaluations).
11. Clarification that all efficacy analyses were conducted on this population and were based on the effective DL/daily doses of Givinostat at which each patient was treated.
12. Correction of typographic mistakes and better explanation of some sentences existing in the clinical study protocol version 2.0 (including Amendment 1, version 1.0, 23rd July 2013), in order to better detail the right procedures to be followed.
13. Update of the safety sections according to the more updated notification of Serious Adverse Event (SAE) Form (i.e. by electronic CRF), Adverse Events definition and the details of the Sponsor’s Drug Safety Unit.

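### Section 5.2 bases all efficacy analyses on the actual dose, leaves it undefined for patients whose dose changes, and conflicts with the assigned-dose and pooled-analysis rules elsewhere in the SAP

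*SAP*

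**What the plan says.** Section 5.2 closes the ITT definition with a rule that has no exception: it covers every efficacy analysis and ties each one to the effective or actual "DL/daily doses of Givinostat at which each patient has been treated". Section 3.7 lists the same rule as point 11 of Amendment 2 ("based on the effective DL/daily doses of Givinostat at which each patient was treated") and names point 11 among those affecting the planned analyses.

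The dose taken may change after baseline:

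- Section 3.4.1, on Part B, makes some changes compulsory for safety: "dose reductions or interruptions are mandated for specific toxicities". It separately permits a later rise for lack of response: "dose increases after an initial dose reduction are allowed in the case of inadequate efficacy at the reduced dosage". Three Part B doses are possible ("i.e. 50 mg b.i.d., 75 mg b.i.d., 100 mg b.i.d").
- Section 3.2.2.3, once the MTD is set: "patients on treatment at lower DLs can be allowed to escalate their Givinostat dose up to the MTD" for the rest of Part A, at the investigator's discretion and with written sponsor authorization.

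Other sections work from the assigned dose or from one pooled group:

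- Sections 3.1 and 3.2: only Part A PV patients "assigned to the dose selected for Part B (MTD) can be counted towards the efficacy assessment in Part B".
- Section 3.4.2: the dose level is assigned at enrolment and written into the permanent patient ID.
- Section 3.3: Part B patients start at 100 mg b.i.d.
- Sections 3.5 and 4: the decisions rest on 12 and 28 patients.
- Section 17.2: Stage 1 is one CR/PR frequency with a 95% CI. The Stage 2 model adjusts for age, sex and disease type and has no dose term.

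**The concern.** Actual dose is a post-baseline variable and, under this plan, partly a consequence of outcome: toxicity lowers it, and inadequate efficacy can raise it again. A response table arranged by dose taken therefore conditions on something related to response. That departs from what an intent-to-treat analysis is meant to do.

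The rule also cannot be programmed as written. It does not say whether the actual dose is the starting, modal or last dose, or the dose at the assessment visit. One patient could sit at different levels at C3D28 and C6D28, and in an open-label trial the choice could be made after responses are known.

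Two results are exposed: Part A response by dose level at C3D28 and C6D28 (Section 18.1), and which Part A patients count toward Stage 1 of Part B (Section 3.5).

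**Working it through.** **1. The Part B design as stated.** Inputs from Section 3.5: null rate 0.50, alternative 0.75; stop if 6 or fewer of 12 respond; reject the null if 18 or more of 28 respond.

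- Early termination under the null = P(X1 ≤ 6 | 12, 0.50) = 0.6128 (SAP 0.613).
- Expected size = 12 + (1 − 0.6128) × 16 = 18.195 (SAP 18.2).
- Rejection probability = Σ over x = 7 to 12 of P(X1 = x) × P(X2 ≥ 18 − x | 16, p). This is 0.0815 at p = 0.50 (0.08148 unrounded; SAP 0.081) and 0.9017 at p = 0.75 (SAP 0.902).

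The SAP's figures are reproduced. They belong to denominators of 12 and 28 and cannot be applied to a subgroup still taking 100 mg b.i.d.

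**2. The same patient under the two rules.**

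| Patient | Assigned or pooled rule (3.1, 3.2, 3.4.2, 3.5, 4, 17.2) | Section 5.2 taken literally |
|---|---|---|
| Part A, starts below 100 mg b.i.d., later escalates to the MTD | Stays at the starting level; not counted in Part B | At the MTD from the change onward |
| Part A, starts at 100 mg b.i.d., later reduced | DL1; may count toward Stage 1 | Off the MTD; Table 1.1 has no label for 50 mg o.d., which Section 3.4.1 allows in Part A |
| Part B, reduced to 75 mg b.i.d. | In the pooled group | At 75 mg b.i.d., which has no label in Table 1.1 |
| Part B, reduced, then re-increased for inadequate efficacy | In the pooled group | Depends on which dose is called actual |

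The first two rows give opposite answers on who counts toward Stage 1. That stage turns on 7 responders out of 12, so one patient can matter.

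**3. What a split by actual dose could do.** The SAP gives no dose-change rates, so this step rests on assumptions. Let p be the true response rate, and let a and b be the shares of responders and non-responders no longer on the MTD. The apparent rate among those still on it is p(1 − a) / [p(1 − a) + (1 − p)(1 − b)].

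| a | b | Apparent rate, p = 0.50 | Apparent rate, p = 0.75 |
|---|---|---|---|
| 0.1 | 0.5 | 0.643 | 0.844 |
| 0.2 | 0.4 | 0.571 | 0.800 |
| 0.3 | 0.3 | 0.500 | 0.750 |
| 0.4 | 0.2 | 0.429 | 0.692 |
| 0.5 | 0.1 | 0.357 | 0.625 |

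At p = 0.50, 30% of patients are off the MTD in every row, leaving about 20 of 28. At p = 0.75 the share off runs from 20% to 40%. The apparent rate can move either way, and does not move when dose change is unrelated to response.

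**4. Part A.** Section 3.7 reports six patients at DL1 and three at DL6. With groups this small, one reassignment is visible. Assume 3 of 6 respond at DL1 (50%). Moving in one escalated patient gives 3/7 = 43% or 4/7 = 57%. Moving out one reduced patient gives 2/5 = 40% or 3/5 = 60%. The SAP does not say whether any patient changed level.

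**The case against.** The strongest reply is that the sentence says efficacy analyses are based on actual dose, not that they are grouped by it, and that the rest of the SAP points the other way.

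- Part B is analysed as one group in Sections 3.5, 4 and 17.2.
- Section 8 takes its labels from Table 1.1, which defines the two DL1 labels as the first three and the additional three patients. A patient who escalates later fits neither.
- Section 3.4.2 fixes the dose level in the patient ID.
- Section 23 tabulates dose changes by dose level in Part A, which makes little sense if the level moves with the dose.
- Presentation by dose level or cohort is limited to Part A in Sections 17.1, 20.1, 20.3 and 20.4.
- The sentence is carried over from Amendment 2, and Part A efficacy is secondary and reported as frequencies.

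Most of this stands. A reader might infer from Section 5.2 that the Simon response rate is itself confounded by outcome, because patients who leave 100 mg b.i.d. drop out of it. The documents do not support that: no section plans a Part B response rate restricted to patients still on that dose. On the pooled reading, the rate describes starting at the MTD with permitted modification. A reader might also infer that the rule flatters the drug, but the direction of any bias is unknown.

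The reply does not remove the conflict. Section 5.2 covers all efficacy analyses, and nothing says that Sections 3.5, 4 and 17.2 override it. Section 18.1 does not state the grouping for Part A response, while Section 8 presents tables by treatment dose level. The evidence that dose level means the assigned cohort is therefore evidence that Section 5.2 is worded wrongly.

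**Conclusion.** The concern holds as an unresolved contradiction together with an undefined variable. It does not show that the primary result is biased. If Sections 3.5, 4 and 17.2 govern, the effect on the pooled Part B response rate is nil and the stated type I error and power are untouched. If Section 5.2 is applied literally, Part A response by dose level at C3D28 and C6D28 would rest on an outcome-related grouping, and membership of Stage 1 would be unclear. The size and direction of the resulting bias cannot be computed from the SAP. The figures in steps 3 and 4 of the working use assumed shares and counts, and show only that a dose-split rate can move either way or not at all. The point is worth correcting because the sentence covers every efficacy analysis and a precise replacement is easy to write.

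**What to change.** Replace the last sentence of Section 5.2 with a rule stating that:

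- ITT and PP efficacy analyses use the assigned starting dose level;
- Part A efficacy is tabulated by starting dose level at both C3D28 and C6D28;
- the Part B Simon decision counts all patients in the analysis set who were enrolled at the Part B dose, including eligible Part A patients assigned to it, whatever their later dose changes;
- any efficacy summary by actual dose is supplementary and descriptive, with a stated derivation (for example, the dose at the assessment visit) and labels for every dose that can occur.

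This changes only how patients are classified for analysis, not the dose-modification rules. The cost is SAP wording, with any actual-dose efficacy tables becoming supplementary. Because Section 3.7 attributes the sentence to Amendment 2, the protocol wording should be aligned, or the change recorded under the planned-analysis heading of Section 3.7, which now lists only the change of software.
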